Specific Aim 1: Examine the effects of intranasal oxytocin (40 IU) vs. placebo on subjective alcohol craving and aggression in response to the Taylor Aggression Paradigm (TAP) among couples with AUD and IPA.

Specific Aim 2: Examine the effects of intranasal oxytocin (40 IU) vs. placebo on physiological (i.e., heart rate, skin conductance) and neuroendocrine (i.e., cortisol,) response to the Taylor Aggression Paradigm (TAP) among couples with AUD and IPA.

Specific Aim 3: Identify predictors of oxytocin response (e.g., gender, endogenous oxytocin, IPA severity).

We hypothesize that individuals who receive oxytocin, as compared to placebo, will demonstrate significantly lower alcohol craving and aggression, as well as lower physiological and neuroendocrine reactivity to the TAP. Furthermore, we hypothesize that oxytocin response will be greater among women as compared to men. While the existing literature examining the effects of endogenous oxytocin and potentially traumatic experiences, such as IPA, on oxytocin response is scant, we hypothesize that oxytocin response will be lower among individuals with higher endogenous oxytocin levels and greater IPA severity.

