At the outset of the TAP procedure, the words "Get Ready" appear on the computer screen in front of the participant. Then the words "Press the Spacebar" appear on the screen. Participants press and hold the space bar until the words "Release the Spacebar" appear on the screen, at which time the participant will release the spacebar as quickly as possible. A "win" is indicated to the participant with the words "You Won. You May Give a Shock" appearing on the screen.

Following a winning trial, participants choose whether or not to shock their opponent and its intensity on a level ranging from 1 (very mild shock, definitely not painful) through 10 (intense shock, definitely painful). A “loss” is indicated with the words “You Lost. You Will Get a Shock” appearing on the screen. The shock intensity received by the participant is randomly selected by the computer software within the calibrated range specified for each participant.

Calibration: The finger stimulator apparatus (Colbourn Instruments, Whitehall, PA) is calibrated for each participant, controlling for individual differences in pain threshold that may influence shock selection. Two electrodes are attached to the participant’s middle and index finger on the non-dominant hand. Each participant is administered 1-second shocks that increase stepwise beginning with the lowest possible intensity. Participants are instructed to inform the researcher when the shocks are first detectable and then again when they experience a shock as painful. During the actual TAP procedure, shock levels range from 1 to 10 and correspond to the participant’s 55% through 100% pain threshold.

TABLE 3. LABORATORY TESTING

Duration	Procedure
Screening portion	
2-2.5 hours	Informed consent and assessment battery
30 minutes	Blood draw from nurse from Research Nexus
Laboratory portion	
Minute 0	Baseline measurement #1 (VAS, HR, BP, cortisol)
Minute 5	Baseline measurement #2 (VAS, HR, BP, cortisol)
Minute 10	Oxytocin or placebo administered
Minute 40	Post-medication assessment (VAS, HR, BP, cortisol)
Minute 45	Alcohol Cue
Minute 50	Post-Cue assessment (VAS, HR, BP, cortisol)
Minute 65	TAP
Minute 70	Immediate post-task assessment (VAS, HR, BP, cortisol)
Minute 85	15-minute post-task assessment (VAS, HR, BP, cortisol)
Minute 100	30-minute post-task assessment (VAS, HR, BP, cortisol)
Minute 130	60-minute post-task assessment (VAS, HR, BP, cortisol)
Minute 135	Participant debriefed, compensated and discharged

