12.0 Data Management and Statistical Analysis Plan

Descriptive statistics will be used to characterize participants at each time point. Because the units of randomizations are dyads (i.e., couples), all analyses will account for potential within-dyad correlation (e.g., intraclass correlation [ICC]). Generalized linear mixed models (GLMMs) with random couple effects will be used to assess group differences in baseline characteristics. These can be operationalized using SAS Proc Mixed and Proc GLIMMIX. Should any variables

exhibit significant departures from normality, variable transformations (e.g., logarithmic) or non-parametric approaches will be used, as appropriate. GLMMs are ideal for handling analyses involving correlated measures¹⁰⁸, and they will allow us to estimate both the between- and within-couple variation. GLMMs are also useful for modeling longitudinal (repeated) outcomes on individual subjects, and the models can be adapted with appropriate link functions for continuous, binary, and count outcomes. GLMMs will be constructed for analyses involving group (or subgroup) comparisons over time. The models will also control for relevant covariates, including baseline outcome levels and number of standard drinks during the 60 days prior to participation. Various covariance structures (e.g., compound symmetry, autoregressive, etc.) will be tested, with final model selection based on fit statistics such as Akaike Information Criterion¹⁰⁹. Analyses will be conducted using SAS v9.4 (Cary, NC).

Hypothesis 1: Participants who receive oxytocin, as compared to placebo, will demonstrate significantly lower craving, aggression, physiological (HR, BP), and neuroendocrine (cortisol) reactivity to the TAP. To test this hypothesis, GLMMs with identity link functions (for continuous measures) and log link functions (for count data) will be used to model the between-group differences. Random couple effects will be used to account for within-couple correlation.

Hypothesis 2: Oxytocin response will be greater among women as compared to men. To test this hypothesis, GLMMs will be used to assess serially measured time points following medication administration (15, 30, and 60 minutes post task). The effects of gender, time, and their interaction will be assessed. Primary outcomes include alcohol craving, aggression, and cortisol.

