Hypothesis 3: Oxytocin response will be lower among individuals with higher endogenous oxytocin levels and greater IPA severity. To test this hypothesis, alcohol craving, aggression, and cortisol levels will be examined as repeated measures variables using the strategies described above. Separate models will be conducted for endogenous oxytocin levels and IPA severity.

Randomization. Participants will be randomized to oxytocin or placebo. Because the extant literature suggests that the frequency and intensity of aggression in the TAP may be higher in men, on average, than women, a stratified randomization scheme will be used to ensure that groups are balanced by gender.

Sample Size Justification. Given the preliminary nature of this investigation, we aim to detect between-group differences in aggression measured by the TAP (oxytocin vs. placebo). Prior work¹¹⁰⁻¹¹² suggests that mean baseline aggression as measured within the TAP ranges from 2 to 4, with a standard deviation of 1.1 and with men having higher scores, on average, than women. With 50 couples (n=100) per group (and assuming alpha=0.05 and 2-sided hypothesis testing), we will have 80% power to detect moderate within-group changes (around 0.4 units [$\pm 10\%-20\%$] on the TAP shock intensity scale), consistent with our study hypotheses. We will have 80% power to detect moderate between-group differences (0.4 units) but with a larger alpha level (0.25), which is consistent with our pilot study framework.

Confidentiality and Data Security. All research personnel will attend a required in-service training conducted by [name] and [name] where the screening, informed consent, and assessment protocols will be described. The study protocol and safety plan will be printed and kept in a central location within the research space for easy access for all research staff. Standard operating procedures (SOPs) for the management of any participant or study-related emergency will be established and research staff will be trained on these protocols. All participant assessments will be scheduled during normal working hours beginning at 8am on the MUSC campus to ensure the presence of clinical staff and the safety of participants and

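### The Hypothesis 2 (gender) model for craving uses only the 15-, 30- and 60-minute post-task readings and leaves out the scheduled immediate one, whose timing against the TAP is itself unclear

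*Combined protocol and SAP*

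**What the plan says.** Hypothesis 2 in section 12.0 states that oxytocin response will be greater in women than in men. Its model takes as repeated outcome "serially measured time points following medication administration (15, 30, and 60 minutes post task", with gender, time and their interaction as the listed effects. Craving, aggression and cortisol are named as primary outcomes.

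Table 3 in section 10.0 schedules four readings labelled post-task: "Immediate post-task assessment (VAS, HR, BP, cortisol" at Minute 70, "15-minute post-task assessment (VAS, HR, BP, cortisol" at Minute 85, "30-minute post-task assessment (VAS, HR, BP, cortisol" at Minute 100 and "60-minute post-task assessment (VAS, HR, BP, cortisol" at Minute 130. Craving is one of the VAS ratings. The same table starts the TAP at Minute 65, and the TAP description in section 10.0 gives a task length of 12-14 minutes.

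Hypothesis 3 (endogenous oxytocin, IPA severity) lists no time points. Its outcomes are to be "examined as repeated measures variables using the strategies described above". Hypothesis 1 lists none either.

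In section 1.0, Aim 1 concerns craving and aggression in response to the TAP. The main hypothesis there predicts lower craving and aggression and "lower physiological and neuroendocrine reactivity to the TAP". Aim 3 asks only for predictors of oxytocin response.

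**The concern.** The reading nominally closest to the reaction is missing from the one moderator model whose time points are spelled out, and no reason is given. Craving is a momentary rating. If the task raises it briefly, and oxytocin acts on that rise, later readings would show a smaller difference between arms and so a smaller gender difference in response. A null gender result for craving could then arise partly from the measurement window. Because Hypotheses 1 and 3 name no time points, no named model commits to using the immediate reading, and the choice stays open until the data are seen.

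**Working it through.** The documents give no power or precision figure for Hypothesis 2 or 3, so there is no stated figure to reproduce. The check is timing arithmetic on Table 3, followed by an illustration under an assumed decay.

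**Which readings are used.** Dosing is at Minute 10. Six readings follow it, at Minutes 40, 50, 70, 85, 100 and 130, and Hypothesis 2 names the last three. Those at Minutes 40 ("Post-medication assessment (VAS, HR, BP, cortisol") and 50 (after the alcohol cue) precede the TAP and cannot measure a response to it. Of the four readings labelled post-task, one is left out.

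**Where the readings fall.** TAP end = 65 + 12 = Minute 77 to 65 + 14 = Minute 79, midpoint Minute 78.

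| Reading | Minute | Minutes from Minute 70 | Minutes from TAP end (77-79) | In Hypothesis 2 |
|---|---|---|---|---|
| Immediate | 70 | 0 | 7-9 before | No |
| 15-minute | 85 | 15 | 6-8 after | Yes |
| 30-minute | 100 | 30 | 21-23 after | Yes |
| 60-minute | 130 | 60 | 51-53 after | Yes |

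The labels are consistent if counted from Minute 70. By the stated start and duration, however, Minute 70 lies inside the task, and the first retained reading comes only 6-8 minutes after it ends.

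**Size under an assumption.** Suppose the oxytocin effect on craving decays exponentially from Minute 78: effect at t minutes = 0.5^(t/h) of the end-of-task effect, where h is the half-life. The retained readings are at t = 85 - 78 = 7, 100 - 78 = 22 and 130 - 78 = 52.

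| h (minutes) | t = 7 | t = 22 | t = 52 | Mean of three | Mean of four, adding t = 0 |
|---|---|---|---|---|---|
| 15 | 0.724 | 0.362 | 0.090 | 1.176/3 = 39% | 2.176/4 = 54% |
| 30 | 0.851 | 0.602 | 0.301 | 1.753/3 = 58% | 2.753/4 = 69% |
| 60 | 0.922 | 0.776 | 0.548 | 2.246/3 = 75% | 3.246/4 = 81% |
| no decay | 1 | 1 | 1 | 100% | 100% |

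The last column assumes that the added reading is taken at the end of the task, which Table 3 as it stands does not show.

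**The case against.** Much of the case on the other side stands.

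- **Hypothesis 3.** A reader might infer that the endogenous-oxytocin and IPA-severity models also use only three readings. The text does not say so. The strategies it refers to may be the general mixed-model approach and not the Hypothesis 2 time points. The restriction is possible but not stated.
- **Recovery instead of reaction.** A reader might infer that the model tests only recovery. The documents do not show that craving has faded by 15-60 minutes. The waiting-room rules in sections 10.0 and 15.0 are safety holds for high ratings, and Table 3 places debriefing at Minute 135, after the last reading. Section 15.0 uses the 15-, 30- and 60-minute ratings to look for persistent craving. On the stated timings, the 15-minute reading is the first one taken after the task.
- **A larger loss.** The same formula with the nominal intervals of 15, 30 and 60 minutes gives 27%, 49% and 68%. Those figures take Minute 70 as the end of the task, which contradicts the stated duration, so they are not used here.
- **Averaging is not forced.** Time and its interaction with gender are in the model, so the 15-minute contrast can be estimated separately. Under the same assumption it keeps 72% to 92% of the end-of-task effect.
- **Reach.** Aggression is scored from shock choices during the TAP and has no serial readings. For cortisol, later samples are defensible. Saliva is also not taken from everyone: the specimen section excludes BMI of 39 or more and start times after 10:00am, and allows omission for contraindications.

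What remains is that the gender model omits a scheduled post-task craving reading, and that nothing in the plan explains the omission.

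**Conclusion.** The point holds for craving in the Hypothesis 2 gender model. It is a possibility for Hypothesis 3, does not apply to aggression and is weak for cortisol. On the illustrative half-lives of 15, 30 and 60 minutes, the retained readings average about 39%, 58% and 75% of the end-of-task effect. This rests on exponential decay from about Minute 78, which the documents neither support nor rule out, and the loss is nil without decay. It would go too far to say that a null gender finding would be an artefact of the window. Nor can the Minute 70 reading be treated as a clean post-task measure while the stated TAP start and duration place it 7-9 minutes before the task ends.

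**What to change.** First reconcile Table 3 (TAP at Minute 65, immediate post-task reading at Minute 70) with the 12-14 minute task duration, so that it is clear whether this reading is taken during or after the task.

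Then amend section 12.0:

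- Use the immediate post-task reading together with the 15-, 30- and 60-minute readings as the repeated craving outcome in Hypotheses 2 and 3.
- Treat time as a categorical factor, so that the immediate contrast can be estimated separately from the later ones.
- State the time points for each outcome, and treat aggression as a single task-level outcome.

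A separate matter should be settled in the same edit. The effects listed for Hypothesis 2 include no treatment term. Adding a reading does not by itself test a gender difference in oxytocin response; that needs treatment-by-gender terms, and their interaction with time for a contrast at one reading.

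The reading is already scheduled, so no new assessment is needed. The cost is a short wording change, the reconciliation of the schedule and one more time level in the model. The change should be made before the data are unblinded, so that the time points are not chosen after the results are known.

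### Hypothesis 2 concerns oxytocin response by gender, but its listed effects omit treatment-by-gender, and its serial model cannot be fitted to aggression

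*Combined protocol and SAP*

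**What the plan says.** Section 12.0 states "Hypothesis 2: Oxytocin response will be greater among women as compared to men". It applies GLMMs to "serially measured time points following medication administration (15, 30, and 60 minutes post task"), then says "The effects of gender, time, and their interaction will be assessed" and "Primary outcomes include alcohol craving, aggression, and cortisol". Treatment group is not among the listed effects, and restriction to the oxytocin arm is not mentioned. The nearest general text is "GLMMs will be constructed for analyses involving group (or subgroup) comparisons over time", which names no interaction. The same general paragraph adjusts models for the pre-dose value of the outcome.

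For Hypothesis 3, "alcohol craving, aggression, and cortisol levels will be examined as repeated measures variables using the strategies described above", and "Separate models will be conducted for endogenous oxytocin levels and IPA severity". No model terms are listed.

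Section 10.0 defines aggression from the shocks a participant chooses during one 30-trial TAP. Table 3 doses at minute 10 and schedules the TAP once, at minute 65. The later rows, for example "15-minute post-task assessment (VAS, HR, BP, cortisol"), and both baseline rows collect VAS, heart rate, blood pressure and cortisol only.

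**The concern.** With a placebo arm, a claim that women respond more to oxytocin than men is a claim about treatment-by-gender, and about treatment-by-gender-by-time for serial outcomes. Gender and gender-by-time effects describe how the sexes differ, whatever they were given. The Randomization paragraph of section 12.0 itself expects men to score higher than women on the TAP. Women would then look less aggressive with no drug effect at all, which is the direction that would be taken as support for Hypothesis 2.

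Hypothesis 3 inherits the gap by referring back, so none of the three predictors named in Specific Aim 3 (gender, endogenous oxytocin, IPA severity) has a stated test of moderation. Separately, one of the three outcomes assigned to the serial model has no serial data and no pre-dose value.

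**Working it through.** **The plan's own figure.** The documents give no power or detectable difference for Hypotheses 2 or 3. The nearest figure is 80% power for a 0.4-unit between-group difference at alpha 0.25. That concerns another contrast and is not relied on here.

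**What the listed gender effect estimates.** Let g be the placebo-arm gap (men minus women), and g + d the gap on oxytocin, so d is the interaction. With equal arms:

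pooled gender effect = ½[g + (g + d)] = g + d/2.

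Adding a treatment main effect does not change this. Gender-by-time estimates how g + d/2 changes over time, so a difference in response that is constant over time does not appear in it.

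**Inputs for the illustration.** From section 12.0: SD 1.1, 50 couples per arm, two-sided alpha 0.05. Assumed, because the documents do not give them: all couples mixed-sex and randomized as couples, no dropout, ICC 0, 0.3 or 0.67, and the sizes of the sex gaps.

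**Aggression, single occasion, no oxytocin effect.** Gender is tested on the 100 within-couple differences:

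SE = 1.1 × √(2(1−ICC)) / √100 = 0.156, 0.130, 0.089.

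Rejection rates (20,000 simulated trials per setting):

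| Test | ICC 0 | ICC 0.3 | ICC 0.67 |
|---|---|---|---|
| Gender, gap 0.25 | 0.351 | 0.477 | 0.796 |
| Gender, gap 0.5 | 0.890 | 0.968 | 1.000 |

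Treatment-by-gender rejects in 0.048 to 0.053.

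**A real interaction missed.** With d = 0.4 and g = −0.2, the pooled effect is −0.2 + 0.4/2 = 0. Gender rejects in 0.045-0.048 of trials and treatment-by-gender in 0.245-0.595.

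**Separate check with three readings** (ICC 0.3, 4,000 trials):
- Same 0.4 effect in both sexes, men 0.5 higher: gender rejects in 99.8%, gender-by-time in 5.2%, treatment-by-gender in 4.2%.
- Effect 0.8 in women and 0 in men, women 0.4 higher on placebo: 4.0%, 5.4% and 95.8%.

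**Craving and cortisol, in SD units, no oxytocin effect.** The model adjusts for the mean of two baselines, with assumed within-person correlation 0.3 to 0.8 and the same ICCs (6,000 trials per setting):
- Stable 0.5 SD sex gap: gender rejects in 15-98%.
- Post-task level differing by 0.25 SD between the sexes: gender rejects in 78-100%.
- Recovery differing by 0.25 SD between the sexes: gender-by-time rejects in 31-100%. A constant gap leaves gender-by-time near 5%.
- Treatment-by-gender and treatment-by-gender-by-time stay at 4.5-5.6% throughout.

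Baseline adjustment therefore does not repair the test.

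**Power of the term that is needed (aggression).**

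SE = 1.1 × √(2(1−ICC)) × √(2/50); detectable difference at 80% power = 2.802 × SE. If partners were randomized independently, the SE is multiplied by √(1+ICC).

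| | ICC 0 | ICC 0.3 | ICC 0.67 |
|---|---|---|---|
| SE, couples randomized | 0.311 | 0.260 | 0.179 |
| Power for 0.4 | 25% | 33% | 60% |
| Detectable difference | 0.87 | 0.73 | 0.50 |
| SE, partners independent | 0.311 | 0.297 | 0.231 |
| Power for 0.4 | 25% | 27% | 41% |
| Detectable difference | 0.87 | 0.83 | 0.65 |

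Both cases are shown because section 12.0 names couples as the unit of randomization in its opening paragraph but participants in its Randomization paragraph.

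**Aggression in the serial model.** The model needs values at 15, 30 and 60 minutes after the task and a pre-dose value. Table 3 provides none of the four. This conclusion needs no simulation.

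**The case against.** The best reply is that this is brevity, not a wrong test. Hypothesis 2 names oxytocin response, and the general sentence on group or subgroup comparisons suggests that treatment is in the model with gender as the subgroup. That is a fair reading, but it gives at most a treatment main effect, and no interaction with treatment is stated in section 12.0. Hypothesis 3 is silent rather than wrong, and the criticism of it is limited to that.

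On aggression, section 13.0, item 11, mentions ANCOVA and Poisson regression, and Hypothesis 1 gives identity and log links, so single-occasion methods do exist in the document. The 30 TAP trials are also repeated measures of a kind. Neither supplies a moderator term, and no trial-level model is described. The sample size paragraph refers to baseline TAP aggression and within-group change, but Table 3 schedules no pre-dose TAP.

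The objections to the illustration are partly right:
- The gaps, correlations and ICCs are assumed, and the document expects a sex gap only for TAP aggression.
- The masking examples need women to be more aggressive than men on placebo, against that expectation, and are tuned to cancel.
- Mixed-sex couples are not an eligibility rule.
- At alpha 0.25, which the plan uses for its between-group comparison, power for the 0.4-unit interaction would be about 56%, 65% and 86%.

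These points affect the size of the error, not the mismatch between hypothesis and test. It is also true that Aim 3 looks for predictors in a study described as preliminary, and that Hypothesis 1 is untouched.

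**Conclusion.** The concern holds: the plan is wrong as written on both counts and must be corrected. The effects listed for Hypothesis 2 cannot separate oxytocin response from ordinary sex differences, Hypothesis 3 states no treatment-by-moderator term, and the serial model with its baseline covariate cannot be applied to aggression. These conclusions rest on the text and on g + d/2 alone.

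The rejection rates depend on the labelled assumptions. They show that, for aggression, even a 0.25-unit gap unrelated to the drug can make the gender test significant in roughly a third to four-fifths of trials, while the correct contrast holds its 5% level.

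**What to change.** - **Hypothesis 2, craving and cortisol:** fit treatment, gender, time and all their interactions. Test treatment-by-gender and treatment-by-gender-by-time. Report the oxytocin-placebo difference with its confidence interval in each gender.
- **Hypothesis 3:** use separate models containing treatment-by-endogenous-oxytocin and treatment-by-IPA-severity, each also by time for craving and cortisol.
- **Aggression, both hypotheses:** use a single-occasion model with treatment, moderator, their interaction and a random couple effect, without the 15, 30 and 60 minute terms or a TAP baseline covariate. Section 10.0 gives four TAP measures, including a count and a proportion, so name the measure and its link.
- **Precision:** state the detectable interaction beside each test, with its alpha, for the unit of randomization actually used.

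The cost is SAP wording and model code, with no change to data collection. The drawback is that the plan must disclose low power for moderation: about 25-60% for 0.4 units on aggression at alpha 0.05 if couples are randomized, and 25-41% if partners are randomized independently.

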of neurobiological risk and protective factors contributing to AUD and aggression, (b) more precisely elucidate associations between risk factors and IPA compared to existing daily diary and experience sampling methods^{5,39}, (c) examine aggression among both partners simultaneously, and (d) inform effective treatment development for AUD and IPA.

Oxytocin may help reduce craving and aggression. Accumulating evidence suggests that oxytocin may help reduce the effects of social stress on alcohol use behaviors^{49,56}. Few studies, however, have investigated the effects of oxytocin on human aggression. Oxytocin may help reduce IPA by reducing its known precipitating factors such as alcohol use, stress reactivity, and negative affect and by enhancing positive affect. No studies to date have examined the effects of oxytocin among individuals with AUD and co-occurring IPA. Further, accumulating evidence suggests that individual and contextual differences may influence concentrations of endogenous oxytocin and its effects on human behavior⁵⁷. The proposed study will address critical gaps in the literature by utilizing a well-controlled human laboratory paradigm (Taylor Aggression Paradigm) to examine the ability of oxytocin to reduce craving and aggression among couples with AUD and co-occurring IPA. We will compare subjective, physiological and neuroendocrine responses to the laboratory test within-subjects before and after they receive oxytocin or placebo, and between-subjects who receive either oxytocin or placebo. We will also examine individual, dyadic, and contextual factors that may influence oxytocin's effects on craving and aggression, which will help inform future translational research focused on the use of oxytocin among AUD and IPA populations.

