(8) For studies in which alcohol is administered, the DSM plan must indicate that NIAAA guidelines for the administration of alcohol will be followed. These guidelines can be found at the following web address: <http://www.niaaa.nih.gov/research/guidelines-and-resources/administering-alcohol-human-studies>.

The proposed study does not involve alcohol administration.

(9) If the study has a follow-up phase, there must be a specific plan for referral to treatment during follow-up of any patient requiring additional intervention due to significantly increased alcohol consumption or serious psychiatric/medical symptoms.

The proposed study takes place during one study visit and does not include a follow-up phase. All participants will be provided with a list of community resources upon study completion. Ineligible individuals presenting with serious mental or physical health symptoms including acute alcohol withdrawal will be referred clinically.

(10) The DSM plan must indicate that all adverse events and unanticipated problems during follow-up will be reported (SAEs within 48 hours) to the IRB and NIAAA.

Not applicable, as the proposed study does not include a follow-up phase.

(11) The DSM plan must briefly describe the procedures for data quality assurance and confidentiality.

A data analytic plan is outlined in the Data Analysis section. Because this study is a preliminary test of a new medication, we are interested in examining a broad range of outcome variables. The main outcome variables include alcohol craving, aggression, and subjective, physiological, and neuroendocrine reactivity to the laboratory procedure. Outcome data will be analyzed using chi-square, ANCOVA, and Poisson regression models. The alpha level for statistical significance will be set at .05.

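### Hypotheses 2 and 3 imply nine moderator tests with no order, adjustment, stated alpha or exploratory label, so at .05 the chance of at least one false predictor of oxytocin response is roughly 17% to 37%

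*Combined protocol and SAP*

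**What the plan says.** Specific Aim 3 in Section 1.0 is to "Identify predictors of oxytocin response (e.g., gender, endogenous oxytocin, IPA severity"). Section 1.0 gives each named moderator a direction: a greater response in women, and a lower response with higher endogenous oxytocin and with greater IPA severity.

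Section 12.0 carries these forward as Hypotheses 2 and 3, numbered and laid out like the treatment hypothesis.

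- **Hypothesis 2 (gender).** The model terms are given as "The effects of gender, time, and their interaction will be assessed". The outcomes are given as "Primary outcomes include alcohol craving, aggression, and cortisol".
- **Hypothesis 3 (endogenous oxytocin, IPA severity).** Here "alcohol craving, aggression, and cortisol levels will be examined as repeated measures variables using the strategies described above", and "Separate models will be conducted for endogenous oxytocin levels and IPA severity".

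Neither hypothesis states a significance level. Item (11) of the monitoring plan in Section 13.0 says "The alpha level for statistical significance will be set at .05". The sample size paragraph of Section 12.0 uses .05 for within-group change, and for the treatment comparison says "We will have 80% power to detect moderate between-group differences (0.4 units) but with a larger alpha level (0.25"). That paragraph calls the study preliminary and a pilot. Item (11) also calls it preliminary, to justify a broad range of outcomes.

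No section orders the moderators, adjusts for their number, makes them depend on Hypothesis 1, or labels Aim 3 exploratory.

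**The concern.** Three moderators on three outcomes are nine chances to find a predictor. If each is judged alone at .05, the error rate for the set is well above .05. The plan does not tell a reader whether one nominally significant result confirms a hypothesis or is only a lead.

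This matters because Section 2.0 says the moderator work is meant to inform later translational research, so a false predictor could shape who is enrolled or studied next. With no link to Hypothesis 1, a moderator could also be claimed on an outcome where oxytocin shows no overall effect. Naming a single primary outcome for the treatment comparison would not settle this, because the moderator tests are a separate family.

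A second gap is that the terms written for Hypothesis 2 do not include treatment. A gender-by-time effect shows that men and women differ over time. It does not show that they differ in their response to oxytocin relative to placebo.

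**Working it through.** **The plan's own figures.** The plan gives no error rate or power for any moderator test, so there is no figure to reproduce. Its only calculation is the sample size paragraph. With its SD of 1.1, a difference of 0.4 and 100 people per group, two-sided power at alpha 0.25 without clustering is Φ(0.4 / (1.1·√(2/100)) − 1.150) = Φ(2.571 − 1.150) = 92.2%. It falls to the stated 80% if the within-couple correlation is about 0.67: effective n = 100/1.67 ≈ 60, and Φ(1.992 − 1.150) ≈ 80%. The plan gives no such correlation, so the figure is attainable but cannot be confirmed. It concerns the treatment difference and says nothing about Aim 3.

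**Count of tests.**
- Moderators named in Hypotheses 2 and 3: gender, endogenous oxytocin, IPA severity = 3.
- Outcomes named in each: craving, aggression, cortisol = 3.
- One test per pair: 3 × 3 = 9.

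**Alpha.** .05 two-sided per test, from Section 13.0 item (11). Applying it to Hypotheses 2 and 3 is an assumption.

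**Independent tests, no true moderation.**
- At least one false positive: 1 − 0.95^9 = 37.0%.
- Expected false positives: 9 × 0.05 = 0.45.
- At least one in the hypothesised direction, 2.5% per test: 1 − 0.975^9 = 20.4%.

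**Correlated tests.** The documents give no correlations, so these are assumed. Each row is a simulation of 400,000 multivariate normal draws.

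| Assumed correlation among the nine tests | Any false moderator | Hypothesised direction only |
|---|---|---|
| 0 throughout | 37% | 20% |
| outcomes 0.5, moderators 0 | 33% | 18% |
| 0.5 throughout | 27% | 13% |
| 0.8 throughout | 17% | 8% |

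**If aggression is scored four ways.** The TAP description in Section 10.0 defines four aggression indices, and Hypotheses 2 and 3 choose none. Craving, cortisol and four indices on three moderators give 6 × 3 = 18 tests. The chance of at least one false moderator is then about 40% at correlation 0.5 throughout and 22% at 0.8. It is about 49% to 50% with correlation 0.7 among the indices, 0.3 between other outcomes, and 0 to 0.2 between moderators.

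**Model terms.** Hypothesis 2 uses measurements 15, 30 and 60 minutes after the task. Table 3 in Section 10.0 schedules the TAP once, so its aggression scores have no such series and the aggression model needs its own specification. The nine-test count allows one test per moderator and outcome; separate tests of interactions with time would add to it.

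**The case against.** The best defence is that this is a self-described pilot with three prespecified, directional moderators, and that unadjusted reporting of such results is common. Item (11) of Section 13.0 uses the word preliminary about outcome analysis itself, and Section 1.0 admits that the literature on two of the moderators is thin. The context does lean towards hypothesis generation. But the same item then fixes a significance threshold, and no sentence says how a significant moderator is to be read. The defence supports the proposed label; it does not supply it.

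Several stronger readings are tempting, and the documents do not support them.

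- **That a false predictor is likely.** On nine tests at .05 the chance is at most 37%, so less likely than not.
- **That any significant result would confirm a hypothesis.** The directions are fixed in advance. A significant effect the wrong way contradicts the hypothesis, so the chance of a false confirmation is about 8% to 20%.
- **That the error reaches 60%, or twelve times nominal.** This is 1 − 0.95^18 and needs 18 independent tests. Four indices taken from one 30-trial task are not independent.
- **That the plan sets .05 for these tests.** It does not. The .05 stands in the monitoring plan beside chi-square, ANCOVA and Poisson models, while Section 12.0 uses mixed models and also mentions 0.25. If 0.25 were used, nine independent tests would give 1 − 0.75^9 = 92.5%, but nothing says that it applies to moderators.
- **That the moderator list is unlimited.** Aim 3 introduces its list as examples, and Section 2.0 says "We will also examine individual, dyadic, and contextual factors that may influence oxytocin's effects on craving and aggression". Hypotheses 2 and 3, however, name exactly three.

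**Conclusion.** The point holds as a gap in how Aim 3 is framed and specified. The size is 37% for nine independent tests at .05, about 27% to 33% under moderate correlation and 17% at 0.8, or about 8% to 20% in the hypothesised direction only. These figures assume no true moderation, one test per moderator and outcome, the general .05, and correlations that the documents do not give. Testing all four TAP indices would raise them.

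The omission of treatment from the terms listed under Hypothesis 2 depends on none of these assumptions. A treatment-by-gender term may well be intended, but it is not written, and without it the question in Aim 3 is not answered. The change should be made; it affects what may be concluded about predictors and leaves the conduct of the trial as it is.

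**What to change.** In Section 12.0, do one of the following:

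1. Label Hypotheses 2 and 3 exploratory, report each treatment-by-moderator estimate with a 95% CI, and make no significance claim.
2. Name one confirmatory treatment-by-moderator test in advance, with its outcome (for example treatment-by-gender on TAP average shock intensity), test it at .05, and label the rest exploratory.

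Under either option, write the treatment-by-moderator term into both hypotheses. For Hypothesis 2 this means adding treatment to gender, time and their interaction. State which aggression index is used and, if any test is kept, its alpha.

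The cost is a few sentences, with no new data or participants. The downside is that a nominally significant moderator, other than one named in advance, can be reported only as hypothesis-generating.
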